#### 5.4 Baseline

In all efficacy analyses, baseline is defined as the last non-missing assessment prior to the first dose of ISIS 396443 or first sham procedure.

#### 5.5 Analysis methods for the primary endpoint

The HFMSE is a tool used to assess motor function in children with SMA. The scale was originally developed with 20 scored activities and was devised for use in children with Type 2 and Type 3 SMA with limited ambulation to give objective information on motor ability and clinical progression. The expanded scale includes an additional module of 13 items developed to alleviate the ceiling effect and allow evaluation of higher functioning and ambulatory SMA patients. Each item is scored 0 (unable), 1 (performs with modification or adaptation) or 2 (able) and the total score is calculated by summing the 33 items and ranges from 0 to 66 with higher scores indicating greater motor function. If 6 or fewer items are missing, then these items will be imputed to be 0 when summing all 33 items. If greater than 6 items are missing, then the total score will be set to be missing.

The primary endpoint is the change from baseline HFMSE score at 15 months.

An interim analysis based on the primary endpoint may take place (Sections 5.1 and 5.2) and the analytical methods for the final (Section 5.5.1) and interim analyses (Section 5.5.2) are described.

### **5.5.1 Final analysis of primary endpoint**

#### **5.5.1.1 Main analysis**

The main analysis is to compare the change from baseline HFMSE score at 15 months between the two treatment groups based on the ITT Set. The data will be analyzed using an analysis of covariance (ANCOVA) model with treatment group as a factor and age at screening and baseline HFMSE score as covariates. The null hypothesis is that ISIS 396443 and sham procedure control groups have the same change from baseline HFSME score at 15 months. Missing post-baseline HFMSE data will be handled using the multiple imputation method.

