## **2 Study design**

This is a Phase 3, multicenter, double-blind, randomized, sham-procedure-controlled study of ISIS 396443 administered intrathecally over 15 months to patients with later-onset SMA. Approximately 117 subjects will be randomized 2:1 to receive a 12 mg dose of ISIS 396443 or undergo a sham procedure as control, respectively. Randomization will be stratified based on the subject's age at screening: <6 years versus  $\geq$ 6 years. A separate randomization list will be used for Japan. If a subject does not successfully receive the first dose of ISIS 396443 or undergo the first sham procedure, they will be replaced.

ISIS 396443 will be administered using a loading regimen (dosing on Study Days 1, 29, and 85) followed by a maintenance dosing 6 months thereafter (Day 274). Subjects randomized to the sham-procedure control group will undergo a sham-procedure on Study Days 1, 29, 85, and 274.

No adjustment of dose is permitted. However, should a concurrent illness prevent the dosing procedure from being performed safely, each scheduled dose may be delayed by up to 4 weeks.

The study will consist of screening, treatment, and post-treatment follow-up-periods. The total duration of participation in the study is approximately 16 months.

Blinded safety data will be reviewed on an ongoing basis by the Sponsor and the Medical Monitor. Unblinded safety data will also be reviewed on an ongoing basis by an independent Data Safety Monitoring Board (DSMB) (Section 6.6). In the protocol it was planned that an interim analysis may be conducted when all subjects will have completed the month 6 assessment and at least 39 will have completed the month 15 assessment. An interim efficacy analysis will be conducted using a targeted cut-off date of 31 August 2016 for the clinical data. At the time of the interim analysis, it is expected that approximately 52 subjects will have attended the Month 15 assessment and all 126 subjects will have had the opportunity to attend the assessment at Month 6 (Section 5.1).

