### 5.1 Interim and final efficacy analyses

An interim analysis may take place when all subjects have completed the 6-month assessment and at least 39 subjects have completed the 15-month assessment with a targeted clinical cut-off date of 31 August 2016. At the interim analysis, only the primary endpoint will be tested. The final efficacy analysis will take place when the last subject completes the 15-month assessment or earlier if the study is terminated on the grounds that conducting a sham-controlled study is no longer deemed ethical based on the assessment of risk-benefit of ISIS 396443.

At the interim analysis and final analysis, the same analysis of covariance (ANCOVA) model will be used in analyzing the change from baseline in HFMSE score to month 15. At the interim analysis, the month 15 endpoint values will not be available for some patients, so a multiple imputation method will be used to estimate them ([Section 5.3](#)). This method will also be used in the final analysis for the primary endpoint

The interim analysis results will be reviewed by an independent Data Safety Monitoring Board (DSMB) and an Unblinded Senior Management Team from the Sponsor. Recommendation will be made on whether it is appropriate for the trial to continue according to the current protocol or whether the protocol needs to be modified. During the interim analysis, subjects will continue in the study.

In the protocol it had been planned to conduct the interim efficacy analysis with an alpha of 0.02, however in finalizing this statistical analysis plan it was decided to conduct the interim analysis at a significance level of 0.025. If the study is not stopped at the interim analysis, the final analysis (test and confidence interval estimate procedures) will be conducted at a significance level determined by the resampling procedure as follows.

Let  $T_1$  and  $T_2$  be the standardized test statistics at the interim and final analyses, respectively. In order to determine the alpha level for the final analysis, the correlation between  $T_1$  and  $T_2$  is first estimated based on the resampling approach (Westfall and Young 1993):

- Among the 126 subjects enrolled in the study, randomly assign 84 subjects to the ISIS 396443 group and 42 subjects to the sham control group.
- Apply the re-randomized treatment assignment to the interim data and obtain the standardized test statistics  $T_1$ .

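### The resampling that sets the final alpha, and the age-adjusted models, do not follow the age strata and Japan list used to randomise; the effect is small

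*SAP*

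**What the plan says.** On allocation, SAP section 2 states "Randomization will be stratified based on the subject's age at screening", with the cut at 6 years, and protocol 4.2 agrees. The SAP adds "A separate randomization list will be used for Japan". The ratio is 2:1.

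On the primary model, SAP 5.5.1.1 specifies an "analysis of covariance (ANCOVA) model with treatment group as a factor and age at screening and baseline HFMSE score as covariates". The logistic models for the binary secondary endpoints (SAP 5.6.1, 5.6.2, 5.6.5 and, by reference, 5.6.6) adjust for age at screening and a baseline measure. None names the under-6 / 6-or-over indicator. The text does not say outright whether age enters as a continuous variable.

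On the final significance level, SAP 5.1 opts to "conduct the interim analysis at a significance level of 0.025". The correlation of the interim and final test statistics, T1 and T2, "is first estimated based on the resampling approach". Each of 10,000 resamples is instructed to "randomly assign 84 subjects to the ISIS 396443 group and 42 subjects to the sham control group", with no mention of strata or of the Japan list. The correlation then goes into a bivariate normal equation that gives the final cut-off c2.

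**The concern.** A re-randomisation procedure should reproduce the scheme that generated the assignments. Here the written rule permutes across age strata and across the Japan list, and fixes 84:42 overall instead of using the counts realised within each list and stratum. This step is confirmatory: if the primary endpoint is not significant at the interim, it decides the alpha at which that endpoint is tested at the end.

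The models raise a related point. Stratification forces balance on the under-6 / 6-or-over split. Linear age captures the difference between strata fully only if mean change in HFMSE is linear in age over the eligible range of 2 to 12 years. If there is a step near age 6, part of it stays in the residual and some precision is given up.

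**Working it through.** **1. The plan's own figure.** SAP section 9 gives 70 treated and 35 control, a 3-point difference, SD 4.4, two-sided alpha 0.05, and at least 90% power.
- SE = 4.4 × √(1/70 + 1/35) = 0.911
- 3 / 0.911 = 3.29; power = Φ(3.29 − 1.96) = 0.909, or 0.904 with the t distribution

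The claim reproduces. It is the only precision statement available: the documents give no standard error for the treatment effect. At 84:42 the unadjusted reference value is 4.4 × √(1/84 + 1/42) = 0.832.

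**2. Design set beside analysis.**

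| Feature | Randomisation | ANCOVA and logistic models | Resampling in 5.1 |
|---|---|---|---|
| Age under 6 / 6 or over | Stratum | Age at screening only | Not used |
| Japan list | Separate list | Not used | Not used |
| Numbers per arm | 2:1 | – | 84:42 in one pool |

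**3. Is the model standard error right under stratified allocation?** Simulation used 126 subjects, 2:1 permuted blocks of 6 within stratum, no treatment effect, residual SD 4.4, complete data and 4,000 trials per scenario. The age effects and the share under 6 are assumptions. The eight scenarios below are those completed of 15 planned.

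| Under 6 | Step at 6 (points) | Slope per year | Linear age: empirical SD / model SE | Type I error | With stratum: model SE | Type I error |
|---|---|---|---|---|---|---|
| 50% | 0 | 0 | 0.829 / 0.834 | 0.0530 | 0.836 | 0.0525 |
| 50% | 0 | −0.5 | 0.853 / 0.835 | 0.0520 | 0.838 | 0.0530 |
| 50% | −3 | 0 | 0.855 / 0.845 | 0.0517 | 0.836 | 0.0515 |
| 50% | −3 | −0.5 | 0.844 / 0.847 | 0.0512 | 0.837 | 0.0508 |
| 50% | −6 | 0 | 0.879 / 0.881 | 0.0483 | 0.835 | 0.0568 |
| 75% | 0 | 0 | 0.834 / 0.833 | 0.0478 | 0.836 | 0.0485 |
| 75% | 0 | −0.5 | 0.842 / 0.834 | 0.0560 | 0.836 | 0.0555 |
| 75% | −3 | 0 | 0.840 / 0.844 | 0.0522 | 0.837 | 0.0517 |

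Monte Carlo error is √(0.05 × 0.95 / 4000) = 0.003 for the type I error and about 0.84 / √8000 = 0.009 for the empirical SD. Within that error the linear-age model is calibrated. Only a model with no age term at all went wrong (50% under 6, step −3, slope −0.5: SE 0.994 against an empirical 0.850, type I error 0.021), and the SAP does not use that model.

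**4. Precision from adding the stratum.** A second set of 4,000 trials per scenario, with ages skewed young, gave these mean model standard errors:

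| Age effect | Linear age | Plus stratum | Change in SE | Power for 3 points, alpha 0.05 |
|---|---|---|---|---|
| Step −2 | 0.8411 | 0.8384 | −0.3% | 94.6% to 94.7% |
| Step −3 | 0.8460 | 0.8363 | −1.1% | 94.4% to 94.8% |
| Step −4 | 0.8561 | 0.8379 | −2.1% | 93.9% to 94.7% |
| None | 0.8332 | 0.8356 | +0.3% | – |

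Power is Φ(3/SE − 1.96). Under no, linear or smooth age effects the extra term costs about 0.1–0.3% of the SE.

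**5. Final alpha.** Solve Pr(|T1| ≥ c1 or |T2| ≥ c2) = 0.05 with interim alpha 0.025, so c1 = 2.24. The final alpha is 0.0319 at a correlation of 0.65, 0.0334 at 0.70 and 0.0351 at 0.75.

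At the interim "approximately 52 subjects will have attended the Month 15 assessment", so Month 15 was treated as observed for 52 of 126 and imputed for the rest. Further assumptions: Month 6 to Month 15 residual correlation 0.7, 50–85% of children under 6, and one conditional-mean regression by arm in place of 100 MCMC imputations. The Japan list was not simulated.

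| | One pool | Within age stratum |
|---|---|---|
| Mean correlation, 9 scenarios | 0.694–0.750 | 0.694–0.755 |
| Final alpha | 0.0332–0.0351 | 0.0332–0.0353 |

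The largest average shift within a scenario was 0.03349 to 0.03389, or 0.0004. The largest correlation difference in one simulated dataset was 0.064, partly Monte Carlo noise, worth about 0.002 in alpha. For scale, 10,000 resamples at a correlation of 0.70 carry a Monte Carlo error of (1 − 0.49) / 100 = 0.005. At (0.0334 − 0.0319) / 0.05 = 0.03 of alpha per unit of correlation, that is about 0.00015.

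**The case against.** The strongest reply is that the SAP has not overlooked age. Age at screening is a covariate in every model at issue, and the two-level stratum is only a coarsening of it. SAP 5.7.5 even calls age at screening the stratification factor, and the under-6 / 6-or-over split is used for milestone imputation (5.6.2) and subgroups (5.8). Choosing the underlying variable, the cut, or both is a modelling decision. The gains in step 4 need a discontinuity exactly at age 6, the shape most favourable to the indicator, and nothing in the documents supports one. Even then, power moves by less than one percentage point. All of this stands, and it limits the point to design consistency and a possible small gain.

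A reader might go further and infer that the primary standard error is wrong, or that type I error is not controlled, because the design is ignored. The documents do not support that. No standard error is stated. The resampling produces neither a standard error nor a p-value; those come from model fits combined over 100 imputations (SAP 5.3). With age in the model, the simulated standard error agreed with sampling variability.

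The reply does not remove two things. The rule in 5.1, as written, is not the allocation used. And the loose wording on age leaves room for two programmers to fit different primary models: SAP 5.5.1.1 reads as continuous, while 5.7.5 and 5.8 attach the same words to the two-level factor.

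**Conclusion.** The point holds as a mismatch between design and analysis with a small numerical effect. Permuting in one pool instead of within age stratum changes the final alpha by at most about 0.0004 on average within a scenario. It matters only if the primary endpoint is carried to the final analysis, because SAP 5.2 does not retest it after a significant interim. Leaving out the stratum costs about 1–2% of the standard error if mean change drops 3 to 4 points at age 6. Otherwise including it costs about 0.1–0.3%.

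These sizes rest on assumed age distributions, age effects and visit correlation, on complete data for the standard-error runs, and on a simplified imputation for the alpha runs. The effect of the Japan list was not quantified. SAP 5.8 anticipates 8 subjects there, 8/126 = 6% of the total, so a large effect is not expected. This is a low-priority correction, worth making because it is nearly free and sits in the step that sets a confirmatory threshold.

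**What to change.** - **SAP 5.1:** re-randomise within each combination of randomisation list (Japan, other) and age stratum, keeping the realised number per arm in each. State whether the Japan list was itself split by age.
- **SAP 5.5.1.1 and the secondary-endpoint ANCOVAs:** add the under-6 / 6-or-over stratum as a factor and state that age at screening is continuous. SAP 5.1 requires the same ANCOVA at interim and final, so the change applies to both.
- **Logistic models:** add the same factor where responder counts allow. SAP 5.6.2.1 already switches to Fisher's exact test when either group has fewer than 5 responders, and sparse milestones may not support another term.

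The cost is one model term with one degree of freedom, one line of resampling code and a few words of SAP text, settled before unblinding. At worst it adds about 0.3% to the standard error. Trial conduct and data collection do not change.

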(Cho and Dreyfuss 2010). One (1) of the 5 nucleotide differences between *SMN1* and *SMN2*, a C to T substitution occurs in Exon 7 of the *SMN2* gene resulting in an alternative splicing pattern that favors skipping of Exon 7. The result is that as much as 90% of the transcripts produced from *SMN2* are missing Exon 7. The remainder, *SMN2* transcripts containing Exon 7, produces a full-length (FL) protein product identical to the *SMN1* protein, since the C to T substitution is silent. Humans have a variable copy number of the *SMN2* gene (0-8 copies) (Wirth et al. 2006). The number of *SMN2* copies and the resulting amount of FL-SMN protein expressed in SMA patients (10-40% of normal SMN protein levels) correlates with SMA disease severity and thus *SMN2* is a key modifier of disease phenotype (Covert et al. 1997; Feldkotter et al. 2002; Lefebvre et al. 1997; Prior et al. 2004).

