### **4.2 Demographic and baseline disease characteristics**

Baseline data (demography, medical history, SMA history, baseline disease characteristics, baseline quality of life) will be summarized.

Demography includes age, sex, ethnicity and race. Medical history will be coded in MedDRA and the number and percentage of subjects with each history by preferred term presented, including the presence of scoliosis and presence of contractures. SMA history includes age of symptom onset, time from disease onset to enrollment, age at SMA diagnosis, time from diagnosis to enrollment, number of copies of the SMN2 gene, highest motor function achieved, current motor function, wheelchair use, and amount of physical therapy.

Baseline disease characteristics will be assessed by weight, height, ulnar length, weight for age, height for age, HFMSE, motor milestones, Upper Limb Module Test. These assessments are further described in the next paragraph and Section 5.

Weight for age and height for age will be summarized using the WHO child growth standards (WHO Child Growth Standards, 2006) for subjects aged up to 5 years and similarly the WHO growth reference data (WHO, 2007) for older subjects. These standards comprise percentiles for weight and height for age by sex and are available on a website ([www.who.int](http://www.who.int)) in txt files. Subjects will be cross referenced with these files, given the age and sex of the subject to determine below which percentile they lie for each parameter. The frequency and percentage will then be summarized for each of weight for age and height for age in the following categories:  $\leq 1^{\text{st}}$ ,  $\leq 3^{\text{rd}}$ ,  $\leq 5^{\text{th}}$ ,  $\leq 15^{\text{th}}$ ,  $\leq 25^{\text{th}}$ ,  $\leq 50^{\text{th}}$  and  $> 50^{\text{th}}$  percentile. The standards do not provide weight for age percentiles for subjects aged  $> 10$  years since this is not an appropriate measure due to the confounding effect of the pubertal growth spurt. Therefore, subjects aged  $> 10$  years at baseline will not be included in the summary for this parameter.

Baseline quality of life and caregiver burden of SMA will be assessed by PedsQL and ACEND, respectively.

Demographic, baseline disease characteristics, and baseline quality of life will be presented for the ITT Set, PPS and the Safety Set as appropriate.

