#### *Multiple imputation for HFMSE , upper limb module test endpoint, PedsQL and ACEND*

Since month 15 HFMSE score values will not be available for many of the patients at the interim analysis, missing data will be handled using the multiple imputation (MI) method (Schafer 1997; Schafer 1999). The same method for imputation of missing values will be used at the final analysis.

The imputations will be performed on total scores for baseline and post-baseline visits. The Markov Chain Monte Carlo (MCMC) method will be used under the multivariate normality assumption to impute the missing score by treatment group. The treatment variable will be coded so that the ISIS 396443 group is the first in the sort order and therefore as the MI procedure is by treatment the imputation will be performed on ISIS 396443 subjects first.

Prior to the Proc MI step the dataset will be sorted by treatment and then ascending unique subject identifier (USUBJID). The variable list for imputations will include the baseline total score, age at consent, as well as all available post-baseline total scores. A set of 100 complete imputed data sets will be generated and the relative efficiency (RE) parameter will be checked. The RE is a very common parameter used in MI to determine the acceptability of the imputed results. Regarding the number of imputations, since the sample size in this study is relatively small and proportion of missing information is large, it will be important to run a large number of imputations to get an RE that is close to 98% or higher.

For PedsQL and ACEND the imputation will be performed independently on each dimension or summary score (constructed using all, or a subset of dimensions) separately, rather than at the item level.

The following pseudo SAS code and seeds will be used to perform the multiple imputation.

```
proc mi data =in_data    seed = x n impute = 100 out= imp_data;
  mcmc chain = multiple;
  var base age D92 D169 D274 D365 D456;
  by treatment;
  run;
```

---

Endpoint	Seed
HFMSE	25980495
Upper limb module test	47886416
PedsQL Core Parent	
Physical functioning	12676424
Emotional functioning	35764041
Social functioning	85032085
School functioning	79256650
Psychosocial health summary	74500750
Total Score	51407567
PedsQL Core Patient	
About my health and activities	48001267
About my feelings	21787096
How I get along with others	95088062
About School	11511569
Total Score	13067474
PedsQL Neuromuscular Parent	

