#### **5.5.1.2 Sensitivity analyses**

Several sensitivity analyses will be performed for the final analysis of the primary endpoint.

In the first, the main analysis will be repeated using the dataset from multiple imputation of the missing data in the ITT Set, to compare treatment groups using the PPS.

In the second, the analysis will be performed using a Mixed Effects Model with Repeated Measures (MMRM) with an unstructured covariance matrix, where the treatment group, time (as a categorical variable), treatment by time interaction, and patient age at screening will be included in the model as fixed effects; patient will be a random effect; baseline HFMSE and baseline by time interaction will be included as a covariate. No imputation for missing visit data will be performed and the analysis will be performed on the ITT Set.

In the third sensitivity analysis, only the subset of subjects in the ITT Set who have non-missing values at 15 months will be analyzed using the same ANCOVA model as for the main analysis, in essence an analysis of ‘completers’.

In the fourth sensitivity analysis the missing Month 15 values will be imputed by ‘last observation carried forward’. This will be performed on the ITT set and data will be analyzed by analysis of covariance with treatment group as the factor and subject age at screening and baseline value as covariates.

In the fifth sensitivity analysis the main analysis using multiple imputation will be repeated but for subjects who have a missing 15-month assessment and discontinue due to treatment failure or death the worst of the last observed value or the baseline value will be imputed.

The reasons for treatment termination are captured in the CRF in several categories as: ‘Investigator judgment’, ‘Voluntary withdrawal’, ‘Pregnancy’, ‘Ineligibility’, ‘Protocol deviation’, ‘Adverse Event’ or ‘Other’, and a free text field captures further detail. Therefore, a blinded medical review will be conducted, prior to unblinding to adjudicate if any are due to treatment failure. This list will then be used in determining a subject’s response.

From each imputation method, the data will be analyzed by analysis of covariance with treatment group as the factor and subject age at screening and baseline value as covariates.

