### 5.8 Subgroup analyses

The main analysis for the primary endpoint and each secondary endpoint will be presented for the following subgroups:

- geographic region (North America, Europe and Asia-Pacific).
- below and above the stratification factor used in the randomization (Age at screening < 6 years versus  $\geq 6$  years)
- Disease duration (time from SMA onset to Screening in months) by tertiles

The difference between treatments for continuous endpoints and the proportion of responders in each treatment group and the odds ratio for the binary endpoints will be presented.

If the number of subjects in a subgroup is too small (e.g., < 15% of total number of subjects in the ITT population), the analysis in that subgroup may not be performed. In the event an interim analysis is performed then subgroup analyses will be performed but the number of subjects with a Month 15 value within a subgroup will be assessed and if <40% of subjects have a Month 15 value then these may not be presented. No statistical tests will be performed in the subgroups.

It is anticipated that 8 subjects will be enrolled in Japan and a separate set of tables and listing will be presented for Japanese subjects.

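### SMN2 copy number is planned for every child but has no prespecified role in the HFMSE models or subgroups: a near-free improvement, not an error

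*SAP*

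**What the plan says.** **Role of SMN2.** Protocol 2.1 links copy number and the resulting SMN protein to severity and concludes that SMN2 "is a key modifier of disease phenotype". Section 2.2 builds the treatment rationale on that link, and 2.3.1 says that the drug binds the SMN2 transcript.

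**Collection.** Protocol Appendix A lists copy number at screening. Footnote 12 limits the test to children without a documented result, so the plan is to have a value for everyone.

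**Use in the SAP.**
- Section 4.2 lists "number of copies of the SMN2 gene" among the SMA history items to be summarised at baseline. It also allows adjustment if the groups look different on something clinically important, but names no variable, threshold or model.
- Section 5.5.1.1 fits the primary ANCOVA "with treatment group as a factor and age at screening and baseline HFMSE score as covariates".
- Section 5.5.1.2 adds no SMN2 term in any sensitivity analysis. In the MMRM, "treatment by time interaction, and patient age at screening will be included in the model as fixed effects", together with treatment, time, baseline and baseline by time.
- Section 5.3: "The variable list for imputations will include the baseline total score, age at consent, as well as all available post-baseline total scores".
- Section 2: "Randomization will be stratified based on the subject's age at screening". There is no other stratification factor.
- Section 5.8 has three subgroup factors: region, the age stratum, and "Disease duration (time from SMA onset to Screening in months) by tertiles".

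**The concern.** The protocol singles out one baseline variable as modifying the disease, the drug acts on that gene, and the value is due to be on file. The SAP then gives it no prespecified place in an efficacy analysis. Three things are at stake, all modest:

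- **Precision.** If copy number predicts 15-month change beyond age and baseline HFMSE, leaving it out makes the residual variance larger than it need be.
- **Chance imbalance.** Neither stratification nor the model protects against an uneven split of copy number between arms. The open clause in SAP 4.2 would let an adjustment be chosen after the imbalance is seen, which is weaker than naming it now.
- **Effect modification.** On the sponsor's own rationale, copy number is a natural subgroup to prespecify. If it is examined only after unblinding, the result will be post hoc.

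**Working it through.** **1. The plan's own figure.** Protocol 10.2 and SAP 9 give 70 treated and 35 control, a 3-point difference, SD 4.4 and two-sided alpha 0.05.

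SE = 4.4 × √(1/70 + 1/35) = 0.911, and 3/0.911 = 3.29. Power is 90.4% by noncentral t (103 df) and 90.9% by normal approximation. The stated figure of at least 90% reproduces.

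**2. Enrolled size and test levels.** SAP 5.1 uses 126 children, 84:42, and an interim level of 0.025. The final level is not fixed; it comes from the equation in SAP 5.1 once the correlation between the two test statistics has been estimated. Solving that equation gives 0.029, 0.033, 0.037 and 0.043 at correlations of 0.5, 0.7, 0.8 and 0.9. I use 0.035 as an assumed final level.

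**3. Gain from adding copy number.** Let r be the partial correlation of copy number with 15-month change, given age and baseline HFMSE. The documents give no value, so r is a range of assumptions. Residual SD = 4.4 × √(1 − r²), and SE = residual SD × √(1/84 + 1/42). Power is by noncentral t with 121 df. Equivalent extra children = 126/(1 − r²) − 126.

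| r (assumed) | Residual variance saved | SE | Power at 0.035 | Power at 0.025 | Equivalent extra children |
|---|---|---|---|---|---|
| 0 | 0% | 0.832 | 92.9% | 90.8% | 0 |
| 0.1 | 1% | 0.827 | 93.1% | 91.1% | 1 |
| 0.2 | 4% | 0.815 | 93.8% | 92.0% | 5 |
| 0.3 | 9% | 0.793 | 94.9% | 93.3% | 12 |
| 0.4 | 16% | 0.762 | 96.3% | 95.1% | 24 |

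The lost degree of freedom costs less than 0.01 power points. The 0.025 column uses the interim level but assumes complete data on all 126. At the interim, SAP 2 expects about 52 observed Month 15 values, leaving 126 − 52 = 74 to impute, so that column is not the interim power itself.

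**4. Chance imbalance.** Suppose a copy-number category holds 20% of children (assumed). The SD of the difference in its share between arms is √(0.2 × 0.8 × (1/84 + 1/42)) = 0.076. An imbalance of 1.96 SD is therefore about 15 percentage points. If that category differs in prognosis by 1 to 3 HFMSE points (assumed), the estimate unadjusted for copy number shifts by about 0.15 to 0.44 points, against a 3-point target.

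**5. Subgroup precision.** With 20% of 126 = 25.2 children split 2:1 (16.8 and 8.4), SE = 4.4 × √(1/16.8 + 1/8.4) = 1.86. Multiplied by a t value of 2.07, this gives a 95% CI half-width of about 3.8 points. The 15% size rule in SAP 5.8 falls at 0.15 × 126 = 18.9 children.

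**The case against.** The best defence is that the plan is sound as it stands. An ANCOVA with the baseline score and the variable behind the stratification is standard, and randomisation keeps it valid without SMN2. A reader might infer that the primary test is biased or underpowered. The documents do not support that: type I error is unaffected and the stated power reproduces.

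A reader might also infer that the sponsor calls copy number the determinant of outcome, or prognostic for 15-month change. It does not. Protocol 2.1 and 2.2 speak of correlation with onset and severity across SMA. Eligibility already narrows the phenotype (onset after 6 months, sits, never walked, HFMSE 10 to 54), and age and baseline HFMSE may carry much of the same information. The partial r could be close to zero. This stands, and it is why the gain is shown as a range.

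The SD of 4.4 is the planning SD for a t-test on change, not the residual SD after age and baseline. If those covariates already explain variance, power without SMN2 is higher than shown and there is less to gain. This stands too.

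An SMN2 subgroup would be imprecise, and 5.8 does no subgroup tests. That is true, but the subgroups already listed are also descriptive and under the same size rule.

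Finally, SAP 4.2 tabulates copy number and allows adjustment. This meets the point only in part, since the choice of variable and model is left open until the data are seen.

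**Conclusion.** The point holds as a free improvement, not as an error. Copy number is planned for every child, is tied by the protocol to disease phenotype, and has no prespecified efficacy role in the SAP.

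At the planned 3-point effect, 84:42 and SD 4.4, the gain is about 0.2 to 3.4 power points at an assumed final level of 0.035, for an assumed partial r of 0.1 to 0.4. It shrinks towards zero if age and baseline HFMSE already hold the information. A larger gain could be shown by powering for an effect below 3 points, but no smaller effect is in the documents.

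The other benefits are protection against a shift of perhaps 0.15 to 0.44 points under the assumed imbalance, and a subgroup named before unblinding. Availability for every child is what the schedule plans; no text requires the result before randomisation or covers a missing one.

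**What to change.** Before interim unblinding, amend the SAP as follows:

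1. **Model (5.5.1, 5.5.2).** Prespecify SMN2 copy number as one numeric covariate in the HFMSE ANCOVA. Either put it in the main model at interim and final and keep the current model as a sensitivity analysis, or, at minimum, add a named sensitivity ANCOVA that includes it.
2. **Imputation (5.3).** Add copy number to the HFMSE variable list. Otherwise imputed Month 15 values would understate its association with outcome, which matters most at the interim, and the imputation and analysis models would disagree.
3. **Missing copy number.** State one simple rule that keeps the child in the ITT Set, for example substituting the overall median regardless of arm.
4. **Subgroups (5.8).** Add copy number in pooled categories, descriptive only and subject to the 15% rule, and note that a 20% category would have a half-width of about 3.8 points.

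The cost is SAP wording, one degree of freedom and one more variable in the imputation model. The 3-point responder analysis in 5.6.1 uses the same imputed datasets, so it would inherit that variable. Changing the main model would also depart from the covariates in Protocol 10.6.3 and should be declared, as the SAP already does for its interim level and its milestone imputation. The sensitivity-only route leaves the protocol's ANCOVA covariates as they are.
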